11.8 Secondary Efficacy Objectives

The secondary efficacy objectives are to:

- Further evaluate the anti-tumor activity of GEN3009 or the combination of GEN3009 + GEN3013
- Evaluate clinical efficacy

11.8.1 Definition of Response

11.8.1.1 Response in B-cell NHL Other Than CLL

Objective and best response will be classified according to the Recommendations for Initial Evaluation, Staging, and Response Assessment of Hodgkin and Non-Hodgkin Lymphoma: The

Lugano Classification ([Cheson et al., 2014](#)). Subjects with PR and CR are considered as responders while all other categories, including “not evaluable,” are considered as non-responders. Subjects with CR, PR, or SD are considered to be in disease control.

11.8.1.2 Response in CLL/SLL

Assessment of response to therapy will be classified according to iwCLL guideline ([Hallek et al., 2018](#)) and should include careful physical examination and evaluation of the blood and bone marrow. To define the response to therapy, 2 groups of parameters need to be assessed and documented: parameters of group A assess the lymphoid tumor load and constitutional symptoms; parameters of group B assess the hematopoietic system.

Any response to therapy (eg, CR, PR) should be sustained for at least 2 months before using this response in the assessment. In addition, where appropriate, a further assessment of response (ie, marrow assessment) may be performed at least 2 months after the subject has cleared MRD from the peripheral blood.

CR and PR are considered clinically beneficial; all others (eg, SD, nonresponse, PD, death from any cause) will be rated as a treatment failure ([Hallek et al., 2018](#)).

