11.4.1.2 Expansion

For all efficacy analyses the FAS will be used. The RES may also be used for presentation of results, in particular for responder rates while the trial is ongoing.

For GEN3009 monotherapy cohorts in Expansion (R/R DLBCL, FL and CLL cohorts), ORR will be determined per ([Cheson et al., 2014](#)) for lymphomas and per ([Hallek et al., 2018](#)) for CLL. Subjects with PR and CR are considered as responders while all other categories, including “not evaluable,” are considered as non-responders. ORR will be calculated together with its 95% CI. For GEN3009 + GEN3013 R/R DLBCL cohort, CR rate will be summarized. CR rate is defined as the proportion of patients with CR. Analysis will be based on response assessment by Lugano ([Cheson et al., 2014](#)).

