11.8.2 Duration of Response

DoR only applies to subjects whose best objective response is CR or PR and is defined as the number of days from the first documentation of objective tumor response (CR or PR) to the date of first PD or death.

DoR will be censored and summarized in the same way as PFS (section [11.8.4](#)). The detailed censoring rules are specified in the SAP.

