5.3 Categorization of responses

Responses, as assessed by the investigator and Independent Review Committee (IRC; during the Dose Expansion part), will be categorized as follows, using the Lugano [2] or iwCLL [3] classification method. Further details are provided in Appendices 7, 8, 9 and 10 of the protocol (version 4.0).

The date of response (or progression) will be taken to be the initial date where the response (or progression) was identified. That date will be used for all calculations of duration of response, progression-free survival, etc.

In cases where the response is confirmed, the date of response (or progression) will be taken to be the initial date where the response (or progression) was identified. That date will be used for all calculations of duration of response, progression-free survival, etc.

Lugano or iwCLL Result	Complete Response	Overall Response	Disease Control Status
Complete Response or Complete Remission (CR)	Responder	Responder	In Disease Control
Partial Response or Partial Remission (PR), including nodular PR (nPR)	Non-Responder	Responder	In Disease Control
Stable Disease (SD) or No Response	Non-Responder	Non-Responder	In Disease Control
Progressive Disease (PD)	Non-Responder	Non-Responder	Not In Disease Control
Not Evaluable (NE)	Non-Responder	Non-Responder	Not In Disease Control
Missing response	Non-Responder	Non-Responder	Not In Disease Control

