5.3.1 Complete Response or Remission

5.3.1.1 *Complete Response per Lugano criteria, for B-cell NHL excluding CLL*

Subjects meeting CR criteria based on FDG-PET CT (or CT/MRI and FDG-PET when PET CT not available) per the Lugano criteria will be recorded as CR on the CRF.

Those with documented bone marrow involvement at Screening will require a confirmatory bone marrow aspirate and/or biopsy within 30 days, as described in Table 9.1 of the protocol, within 30 days of the initial documentation of CR. If the bone marrow sample shows bone marrow involvement, the initial response of CR will be retroactively changed to PR.

Subjects without documented bone marrow involvement at Screening will not require further confirmation of their classification as complete responder.

5.3.1.2 *Complete Remission per iwCLL criteria, for CLL*

In order to meet CR criteria per the iwCLL, subjects must have a normocellular bone marrow sample, with no CLL cells or B-lymphoid nodules, as described in Appendix 8.

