5.3.2 Partial Response

5.3.2.1 *Partial Response per Lugano criteria, for B-cell NHL excluding CLL*

Subjects achieving partial response per Lugano criteria, whether an initial assessment of PR or an unconfirmed CR which is later changed to PR on the basis of bone marrow involvement, do not require any further confirmation.

5.3.2.2 *Partial Remission per iwCLL criteria, for CLL*

Subjects achieving partial response per iwCLL criteria must meet improvement criteria as specified in Appendix 8 of the protocol. Nodal partial remission (nPR) is defined as subjects in remission with residual nodules or suspicious lymphocytic infiltrates in a bone marrow biopsy which often indicates a residual disease.

Subjects achieving a partial remission per iwCLL criteria may not require a bone marrow assessment if sufficient information on the hematopoietic system is available to determine partial remission.

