5.3.3 Progressive Disease

Progressive disease must be confirmed by 2 consecutive scans, at least 4 weeks apart, as described in protocol 9.2.3.2.

5.4 *Calculation of durations and times to events*

Duration of an event occurring on or after first dose date, in days, is calculated as event end date – event start date + 1.

Durations in weeks will be calculated as durations in days divided by 7.

Durations in months will be calculated as durations in days divided by 30.4375.

Time from initial diagnosis will be calculated in months, from the initial diagnosis of the primary site to the first dose date: (first dose date – date of first diagnosis) /30.4375

Time from last anti-CD20 therapy to treatment with GEN3009 will be calculated in months, from the latest treatment end date of any agent administered as part of the last prior anti-lymphoma treatment that included an anti-CD20 compound to the first dose date: (first dose date – date of last anti-CD20 therapy +1) /30.4375

Total number of months on trial will be calculated as: (last contact date – first dose date + 1)/30.4375

Follow-up time will be calculated, in weeks, as: (date of last disease assessment by investigator – first dose date + 1) / 7.

Total treatment duration will be calculated in days as:

- If last cycle is Cycle 1, 2 or 3: last dose date – first dose date + 7
- If last cycle is Cycle 4 – 9: last dose date – first dose date + 14
- If last cycle is Cycle 10 or later: last dose date – first dose date + 28

Progression-free survival (PFS)

PFS is defined as the time in days from Day 1 of Cycle 1 to the day (+1) of first documented disease progression, or the day (+1) of death due to any cause, whichever comes first. Progression does not require confirmation (per Lugano criteria). PFS censoring will be based on Table C1 in Appendix C in the FDA Guidance for Industry: Clinical Trial Endpoints for the Approval of Non-small Cell Lung Cancer Drugs and Biologics [4].

Duration of response (DOR) will be calculated in days as:

DOR = date of first documented progressive disease or death from any cause – date of first response + 1.

In the absence of progressive disease or death, responders will be censored per the FDA censoring rule utilized for PFS, as presented in Appendix I. First response is defined as first documented occurrence of CR or PR (including any complete responses pending confirmation). DOR will only be calculated for those subjects achieving CR or PR.

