10.1 Primary efficacy analysis

The primary efficacy endpoint for the Dose Expansion part of this trial is the objective response rate (ORR), using the Lugano criteria for lymphoma and iwCLL for CLL. The ORR is considered a secondary efficacy endpoint for the Dose Escalation part. The main analysis of ORR will utilize the FAS.

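### The protocol's 2-month sustained-response rule for CLL is absent from the SAP, so the CLL cohort's primary ORR is defined inconsistently and may be overstated

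*Protocol*

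**What the plan says.** **Protocol.** Section 11.8.1.2, under the heading that defines response, states for CLL/SLL: "Any response to therapy (eg, CR, PR) should be sustained for at least 2 months before using this response in the assessment". Section 11.4.1.2, which describes the expansion primary endpoint, sends the reader to the same cited CLL criteria for ORR and adds that "Subjects with PR and CR are considered as responders while all other categories, including" not evaluable, count as non-responders. It does not repeat the 2-month condition. Appendix 8, the CLL response table, contains no duration criterion. DoR in 11.8.2 runs "from the first documentation of objective tumor response (CR or PR) to the date of first PD or death".

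**SAP.** Section 10.1 makes ORR the primary efficacy endpoint of the expansion part, using iwCLL for CLL, and states no duration condition. The table in 5.3 marks any CR, PR or nodular PR as an overall responder. For CLL CR, 5.3.1.2 says: "In order to meet CR criteria per the iwCLL, subjects must have a normocellular bone marrow sample, with no CLL cells or B-lymphoid nodules". For CLL PR, 5.3.2.2 says: "Subjects achieving partial response per iwCLL criteria must meet improvement criteria as specified in Appendix 8 of the protocol". Neither sets a minimum duration. Section 5.3 also contains a dating rule: "In cases where the response is confirmed, the date of response (or progression) will be taken to be the initial date". It gives no confirmation interval for CLL.

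SAP 1.1 names protocol v4.0 (Amendment 2) as its basis; the protocol supplied is v7.0 (Amendment 5).

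**The concern.** Someone programming the CLL endpoint from the SAP would go from 10.1 to the 5.3 table, then to 5.3.1.2 or 5.3.2.2, then to protocol Appendix 8. The 2-month condition appears at none of these stops. A CLL PR recorded at Week 6 and lost at Week 12 would be a success under the SAP, although 11.8.1.2 says it should not be used. The SAP does spell out confirmation in other places: marrow within 30 days for lymphoma CR, and two scans at least 4 weeks apart for progression. Its silence on CLL is therefore unlikely to be filled in by a reader.

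At stake is the primary endpoint of a 20-subject, single-arm, open-label cohort. If the definition is settled only after the data are seen, the choice could look driven by the results.

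**Working it through.** **1. Passages side by side.**

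| Place | Duration condition for a CLL response |
|---|---|
| Protocol 11.8.1.2 | At least 2 months |
| Protocol 11.4.1.2 (primary ORR) | None repeated |
| Protocol Appendix 8 | None |
| SAP 5.3 responder table | None |
| SAP 5.3.1.2 (CR) | None; marrow finding only |
| SAP 5.3.2.2 (PR) | None; Appendix 8 only |
| SAP 10.1 and 10.1.1 (ORR) | None |
| SAP 2.1 (listed departures from protocol v4.0) | Not listed |

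Every response that meets the protocol rule also meets the SAP rule, but not the reverse. The SAP count is therefore at least as large as the protocol count, and any difference is upward.

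**2. Size per subject.** The documents give no expected CLL ORR, null rate or power, so there is no planned figure to reproduce. With n = 20 (protocol 4.1.2), one response is 1/20 = 5 points. SAP 10.1.1 specifies Clopper-Pearson 95% intervals: lower limit = Beta quantile 0.025 with parameters (x, n − x + 1); upper limit = Beta quantile 0.975 with (x + 1, n − x).

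| Responders | ORR | 95% CI |
|---|---|---|
| 6/20 | 30.0% | 11.9-54.3% |
| 7/20 | 35.0% | 15.4-59.2% |
| 8/20 | 40.0% | 19.1-63.9% |

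Two unsustained responses, an assumed number, would separate the first row from the last. With none, there is no difference.

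**3. How many might be unsustained.** This needs an assumption about DoR. With exponential DoR and median m months, the share lasting under 2 months is 1 − 0.5^(2/m). The last column multiplies that share by an assumed ORR, regardless of duration, of 35%.

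| Median DoR (months) | Share under 2 months | Excess in ORR (points) |
|---|---|---|
| 4 | 29% | 10 |
| 6 | 21% | 7 |
| 12 | 11% | 4 |
| 24 | 6% | 2 |

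**4. What the scan schedule can show.** Protocol 9.2.2.1 places scans at Weeks 6, 12, 18, 24, 36 and 48, then every 24 weeks. Using the SAP's month of 30.4375 days, 2 months = 2 × 30.4375 / 7 = 8.7 weeks. At nominal times:

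| First seen (week) | First scan at least 8.7 weeks later | Gap (weeks) |
|---|---|---|
| 6 | 18 | 12 |
| 12 | 24 | 12 |
| 18 | 36 | 18 |
| 24 | 36 | 12 |
| 36 | 48 | 12 |
| 48 | 72 | 24 |

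The visit windows can change this. A Week 24 scan done 14 days late (Week 26) and a Week 36 scan done 14 days early (Week 34) are only 8 weeks apart. The rule therefore has to be applied to actual dates.

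**5. Cut-off.** SAP 1.2 times the expansion primary analysis by an unspecified sufficient time on study. A response first seen near that cut-off counts under the SAP before 11.8.1.2 would allow it.

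**The case against.** A reader might infer that the SAP sets an opposite rule for ORR, because SAP 5.4 says: "First response is defined as first documented occurrence of CR or PR (including any complete responses pending confirmation". The documents do not support this. That sentence belongs to the DoR definition, fixes only where DoR starts, and agrees with protocol 11.8.2. For ORR the SAP is silent; it does not contradict the protocol outright.

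Four further points have weight.

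- **The protocol is not fully explicit.** The 2-month sentence sits under secondary efficacy objectives and says should, and 11.4.1.2 does not repeat it. Against that, 11.8.1 is where the protocol defines response, and 11.4.1.2 relies on the same CLL criteria. Applying the rule to the primary ORR is the better reading, but the protocol needs to say so.
- **The SAP predates the current protocol.** Whether v4.0 contained the 2-month sentence cannot be seen, and the Amendment 5 log records that Section 11 was revised. The gap may be a failure to update; the correction is the same.
- **Sites might apply the rule themselves.** The primary ORR uses investigator assessment, so investigators could withhold a CR or PR until it has lasted 2 months. Neither document tells them to record it that way, and dating from first documentation implies that the initial response is recorded.
- **The trial is descriptive.** Protocol 11.4.2 formulates no hypotheses, so no test or threshold changes, and the illustrative intervals overlap heavily.

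**Conclusion.** The inconsistency is real. Protocol 11.8.1.2 conditions a CLL response on 2 months' duration, the SAP does not carry the condition, and SAP 2.1 does not declare a departure. Run as written, the SAP can count subjects as primary-endpoint successes whom the protocol would not.

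The direction is certain: upward or no change. The size is not known. It is 5 points per unsustained response at n=20; the two-subject example and the exponential DoR figures are assumptions, not predictions. It would go too far to conclude that the CLL ORR is inflated, because that depends on how many responses fail within 2 months and the documents give no such rate. The conclusion also rests on reading 11.8.1.2 as governing the primary ORR, which is the natural reading but is not stated in 11.4.1.2.

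**What to change.** Update the SAP to the current protocol and make these changes before the CLL data are analysed:

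- In SAP 5.3.1.2, 5.3.2.2 and 10.1, state that a CLL CR or PR counts toward ORR and CR rate only if still met at an assessment at least 2 months later. Keep the date of first documentation, as protocol 11.8.2 and SAP 5.3 already do.
- In protocol 11.4.1.2, add a cross-reference to 11.8.1.2 so that the rule plainly governs the primary ORR.
- State that the first scheduled scan at least 2 months later, by actual dates, is the one that shows it.
- Set the primary CLL cut-off so that responders have had that scan. Otherwise, count responses without it as non-responders and report how many there are.
- Report ORR and DoR for all CR/PR regardless of duration as a sensitivity analysis.

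The cost is text only, with no new visits. CLL ORR may be slightly lower. Late responses need longer follow-up: one first seen at Week 48 qualifies at about Week 72 on scheduled scans. DoR restricted to sustained responders would be longer, because the shortest responses are removed by construction; the sensitivity analysis is there to show that effect.

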11.8.1.3 Definitions of Relapsed/Refractory

Relapsed disease is defined as disease responding (CR or PR) to therapy that have progressed ≥ 6 months after completion of therapy. Refractory disease is defined as disease not responding to therapy that have progressed or disease responding to therapy that have progressed during therapy or within 6 months (< 6 months) of completion of therapy. For CLL, “relapsed disease” is defined as evidence of disease progression in a subject who has previously achieved a CR or PR for ≥ 6 months. “Refractory disease” is defined as treatment failure (not achieving a CR or PR) or as progression within 6 months from the last dose of therapy.

11.8.2 Duration of Response

DoR only applies to subjects whose best objective response is CR or PR and is defined as the number of days from the first documentation of objective tumor response (CR or PR) to the date of first PD or death.

DoR will be censored and summarized in the same way as PFS (section [11.8.4](#)). The detailed censoring rules are specified in the SAP.

11.8.3 Time to Response

TTR is defined as the time from C1D1 to first documentation of objective tumor response (CR or PR). Descriptive statistics will be presented.

11.8.4 Progression-free Survival

PFS is defined as the number of days from C1D1 to of the first documented progression or death due to any cause.

PFS will be censored if no PFS event is observed before the first to occur between: (i) the analysis cut-off date, and (ii) the date when a new anti-neoplastic therapy is started. The censoring date will

be the date of the last adequate tumor assessment prior to cut-off/start of new anti-neoplastic therapy. The detailed censoring rules are specified in the SAP.

PFS will be derived for all subjects and presented graphically as well as summarized using survival analysis methods.

The quartile estimates of PFS from the Kaplan Meier product limit algorithm will be presented. The 2-sided 95% confidence interval will be presented as well. The number of events may be small, and thereby limit use of the Kaplan Meier method to provide reliable information. In this case, descriptive statistics (eg, n, mean, standard deviation, median, minimum and maximum) for PFS will be presented.

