10.2.1 Duration of response

DOR will be derived for all subjects achieving treatment response. The number of subjects achieving treatment response, as well as the numbers subsequently achieving progressive disease or death, and the number censored, will be presented by cohort. Subjects without a documented progression or death will be censored following the rule laid out in Section 5.3.1.

The median DOR and its 95% confidence interval based on Kaplan-Meier estimates will be presented, as well as the first and third quartiles and their confidence intervals. DOR will also be presented graphically, using Kaplan-Meier curves.

The proportion of subjects with ongoing response, together with their 95% confidence intervals, will be calculated at monthly intervals starting at 1 month, based on Kaplan-Meier methodology.

The following pseudocode will be used to analyze duration of response and other similar times to event:

```
PROC LIFETEST data=xxx OUTSURV=s1 TIMELIST=xx CONFTYPE=loglog;
  WHERE COHORT=xxx;
  TIME survtime*censor (xxx) ;
  ODS OUTPUT QUARTILES=q1;
  run;
```

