10.2.3 Progression-free survival

PFS will be summarized, analysed, and presented graphically as described for DOR. Subjects without a documented progression or death will be censored following the rule laid out in Section 5.3.1.

If feasible, PFS analysis may be also stratified by overall MRD status (negative or positive as per definition in Section 10.2.7)

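### When PFS events are few, protocol 11.8.4 calls for a mean, SD and median that cannot handle censoring, in conflict with the SAP's Kaplan-Meier plan

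*Protocol*

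**What the plan says.** Protocol section 11.8.4 gives every subject a PFS time: "PFS will be derived for all subjects and presented graphically as well as summarized using survival analysis methods". For a subject without an event, the censoring date will "be the date of the last adequate tumor assessment prior to cut-off/start of new anti-neoplastic therapy". The main summary is stated without condition: "The quartile estimates of PFS from the Kaplan Meier product limit algorithm will be presented", with a two-sided 95% confidence interval. The section then adds a caution, "The number of events may be small, and thereby limit use of the Kaplan Meier method to provide reliable information", and a consequence: "In this case, descriptive statistics (eg, n, mean, standard deviation, median, minimum and maximum) for PFS will be presented". It gives no number for how few events count as small, and it does not say how censored times enter the mean, SD or median.

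Protocol section 11.8.2 extends this to duration of response: "DoR will be censored and summarized in the same way as PFS".

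The SAP differs. Section 10.2.3 says "PFS will be summarized, analysed, and presented graphically as described for DOR", and section 10.2.1 says "The median DOR and its 95% confidence interval based on Kaplan-Meier estimates will be presented". Section 10.2.1 also plans quartiles with confidence intervals, counts of events and of censored subjects, Kaplan-Meier curves, and monthly Kaplan-Meier proportions with 95% intervals. It has no descriptive fallback. SAP section 1.1 names protocol version 4.0 (Amendment 2) as its basis; the current protocol is Amendment 5, version 7.0.

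**The concern.** The rule applies exactly when most observed times are censored. A raw mean or median has no way to use the information that a censored subject was still progression-free. If all subjects are included, each censored time counts as though progression had happened then, and the result mostly reflects how long subjects have been scanned. If only subjects with events are included, the result describes those who progressed early. In both cases the number carries the label PFS.

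The better the treatment controls disease, the fewer the events, the likelier the rule is to be used, and the further the reported figure falls below the truth. DoR is at least as exposed, because it covers responders only and its clock starts later, at response. Few events is no reason to leave Kaplan-Meier: a wide interval, or a median that is not reached, is the correct report of sparse data.

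**Working it through.** The documents state no PFS median, event target or minimum PFS follow-up, so there is no planned figure to reproduce. The check is what the listed statistics return when events are few.

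**Inputs from the documents.** Monotherapy cohorts of 20 (protocol section 4.1). Scans at weeks 6, 12, 18, 24, 36 and 48, then every 24 weeks (section 9.2.2.1). Censoring at the last assessment (section 11.8.4). Days divided by 30.4375 to give months (SAP section 5.4). The extra day in the SAP's duration formulas is ignored.

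**Worked example (assumed data).** Of 20 subjects, 3 progress, at weeks 6, 6 and 12, and 17 are censored at week 24. In months, week 6 is 6 × 7 / 30.4375 = 1.38, week 12 is 2.76 and week 24 is 5.52.

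- Descriptive rule, all subjects: mean = (2 × 1.38 + 2.76 + 17 × 5.52) / 20 = 4.97 months, SD 1.37, median 5.52 months. The median is simply week 24.
- Kaplan-Meier: PFS at week 24 = (18/20) × (17/18) = 85%. The Greenwood term is 2/(20 × 18) + 1/(18 × 17) = 0.00882, which gives a log-log 95% interval of 60% to 95%. The median is not reached.
- Same 3 events, but the 17 censored at week 48 (11.04 months): the descriptive mean becomes (2 × 1.38 + 2.76 + 17 × 11.04) / 20 = 9.66 months and the median 11.04 months. The week 24 Kaplan-Meier estimate is still 85%.

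The events are identical, yet the descriptive median doubles because the cut-off moved.

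**Simulation (assumed inputs).** Exponential PFS, 20 subjects, events and censoring placed on the protocol's scan times, 4,000 replicates. True medians are 6, 12 and 24 months. Follow-up at cut-off is exactly 3 months, or uniform over 3–6, 3–9 or 3–12 months. The naive median is the raw median over all subjects; entries are averages over replicates.

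| True median (months) | Follow-up (months) | Events of 20 | Naive median | Median assessment follow-up | Kaplan-Meier median reached |
|---|---|---|---|---|---|
| 12 | 3 | 2.9 | 2.8 | 2.8 | 0% |
| 12 | 3–6 | 4.0 | 3.6 | 4.0 | 10% |
| 12 | 3–9 | 5.0 | 4.6 | 5.2 | 20% |
| 12 | 3–12 | 6.0 | 5.2 | 6.1 | 33% |
| 24 | 3 | 1.5 | 2.8 | 2.8 | 0% |
| 24 | 3–6 | 2.1 | 3.8 | 3.9 | 3% |
| 24 | 3–9 | 2.6 | 4.9 | 5.2 | 8% |
| 24 | 3–12 | 3.3 | 5.6 | 6.1 | 9% |

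Doubling the true median from 12 to 24 months moves the naive median by at most 5.62 − 5.21 = 0.41 months. Changing the follow-up window, for a true median of 12, moves it by 5.21 − 2.76 = 2.45 months. For a true median of 6 months it is 2.8 to 4.4 months, but there 5.5 to 10.1 of 20 subjects have events, so the rule might not be invoked with the longer windows.

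**Events only.** If the descriptive statistics were limited to subjects with events, the median would be 2.0 to 4.1 months over all scenarios. That is still well below the true values and barely related to them.

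**The case against.** A reader might infer that the protocol abandons Kaplan-Meier when events are few and has decided to report follow-up time as PFS. The text does not go that far. The Kaplan-Meier quartiles are stated without condition, and the later sentence says that descriptive statistics will be presented, not that they replace anything. Nor does it say that censoring is ignored. That is an inference, though a natural one, since PFS is derived for all subjects and none of the listed statistics accounts for censoring. By contrast, where the SAP means an unadjusted summary it says so, and only for follow-up time (section 8.2).

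A reader might also infer that sound PFS reporting is missing altogether. It is not. The protocol leaves specific details to the SAP, and SAP sections 10.2.1 and 10.2.3 already plan event and censored counts, curves, quartiles, and monthly rates with intervals.

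Nor does the SAP's silence settle the matter. It was written on an older protocol version that is not available here, so the missing sentence may be only version lag. The modifications in SAP section 2.1 do not withdraw the rule, and the later protocol still contains it.

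Finally, the size depends on assumed follow-up. A window starting at zero would look worse (uniform 0–6 months gives a naive median of 2.5 months for a true 12), but protocol section 11 times the expansion analysis for when response can be evaluated in all subjects. At the final analysis, up to 5 years after the last subject's first treatment, events are less likely to be few.

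These points limit the claim but do not remove it. A mean and median labelled PFS mislead beside a Kaplan-Meier curve as well as in its place, and both ways of treating censored subjects fail.

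**Conclusion.** Wrong as written. When events are few, the statistics named in protocol section 11.8.4, and applied to DoR through section 11.8.2, would mostly report assessment follow-up or, if limited to events, the times of early progressors. They also conflict with the Kaplan-Meier-only plan in SAP sections 10.2.1 and 10.2.3.

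For cohorts of 20 with a true median PFS of 12 months, the naive median runs from about 2.8 to 5.2 months as follow-up lengthens from 3 months to a spread of 3 to 12 months. For a true median of 24 months it is nearly the same, 2.8 to 5.6. These figures rest on assumed exponential PFS, assumed medians and assumed follow-up windows. The worked example shows the dependence on the cut-off without a distributional assumption.

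The consequence is limited to reporting. PFS and DoR are secondary in every part of the trial, and no formal hypotheses are stated, so no decision rule, sample size or error rate depends on them.

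**What to change.** Delete the descriptive-statistics sentence from protocol section 11.8.4. DoR is then corrected through its cross-reference in section 11.8.2. The caution about few events can stay if it leads to a sentence such as: *Kaplan-Meier results are reported whatever the number of events; a median that is not reached is stated as such, and interpretation rests on event and censored counts and on fixed-time rates with confidence intervals.*

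The SAP has no fallback to remove. When it is aligned with the current protocol, keep sections 10.2.1 and 10.2.3 as they are and add the wording for a median that is not reached. Numbers at risk under the curves and follow-up by reverse Kaplan-Meier are useful but optional.

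The cost is one protocol sentence and a small SAP alignment. Design, sample size and data collection do not change.
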